8.7.1 Pain Analysis

Both worst pain and average pain are measured from 0 (no pain) to 10 (pain as bad as you can imagine). A positive value of change from baseline indicates increased pain post-baseline as compared with baseline; a negative value indicates reduced pain post-baseline as compared with baseline. Both worst pain score and average pain score along with change from baseline will be summarized separately by treatment arm and by visit. Change from baseline for both worst pain score and average pain score will be analyzed separately using a mixed model, which includes (“Treatment Arm” and “Visit”) plus the interaction term (“Treatment Arm by Visit”), revision type, clinical site, and with subject as a random effect. Least squares (LS) means along with 95% confidence intervals and p-values at each post-baseline timepoint will be presented.

If an overall missing data rate for worst or average pain scores is 10% or greater, then an approach of multiple imputation based on Rubin’s [1976, 1987]^{3,4} for missing data will be used by creating several different plausible imputed data sets and appropriately combining results obtained from each of them. A basic description of the multiple imputation includes:

1. Using SAS procedures including Proc MI and Proc MIANALYZE;
2. Using the fully conditional specification (FCS) method / algorithm [Brand 1999 and van Buuren 2007]^{5,6} which is a linear regression for continuous variables;
3. Including treatment arm, age (≥ 65 or < 65 years), sex, BMI (≥ 35 kg/m² or < 35 kg/m²), race/ethnicity, material used in the TKA revision, and co-morbidities in the imputation model;
4. Creating five imputed datasets [Rubin 1996]⁷;
5. Combining completed-data estimates from five imputed datasets.

The mixed model analysis described above will be repeated based on the imputed data.

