The normalized scores and change from baseline for each subscale will be summarized by treatment arm and by visit. Change from baseline for normalized scores for each subscale will be analyzed using a mixed model, which includes fixed effects (“Treatment Arm” and “Visit”) plus the interaction term (“Treatment Arm by Visit”), revision type, clinical site, and with subject as a random effect. LS means along with 95% confidence intervals and p-values at each post-baseline timepoint will be presented.

If a missing data rate for any subscale is 10% or greater, then an approach of multiple imputation based on Rubin’s [1976, 1987]^{3,4} for missing data for all subscales will be used by creating several different plausible imputed data sets and appropriately combining results obtained from each of them.

A basic description of the multiple imputation includes:

1. Using SAS procedures including Proc MI and Proc MIANALYZE;
2. Using the fully conditional specification (FCS) method / algorithm [Brand 1999 and van Buuren 2007]^{5,6} which is a linear regression for continuous variables;
3. Including treatment arm, age (≥ 65 or < 65 years), sex, BMI (≥ 35 kg/m² or < 35 kg/m²), race/ethnicity, material used in the TKA revision, and co-morbidities in the imputation model;
4. Creating five imputed datasets [Rubin 1996]⁷;
5. Combining completed-data estimates from five imputed datasets.

The mixed model analysis for each subscale described above will be repeated based on the imputed data.

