Both Global Physical Health and Global Mental Health T-Scores and their corresponding changes from baseline will be summarized separately by treatment arm and by visit. Changes from baseline for both Global Physical Health and Global Mental Health T-Scores will be analyzed separately using a mixed model, which includes (“Treatment Arm” and “Visit”) plus the interaction term (“Treatment Arm by Visit”), revision type, clinical site, and with subject as a random effect. LS means along with 95% confidence intervals and p-values at each post-baseline timepoint will be presented.

If a missing data rate for Global Physical Health or Global Mental Health is 10% or greater, then an approach of multiple imputation based on Rubin’s [1976, 1987]^{3,4} for missing data for both Global Physical Health and Global Mental Health will be used by creating several different plausible imputed data sets and appropriately combining results obtained from each of them. A basic description of the multiple imputation includes:

1. Using SAS procedures including Proc MI and Proc MIANALYZE;
2. Using the fully conditional specification (FCS) method / algorithm [Brand 1999 and van Buuren 2007]^{5,6} which is a linear regression for continuous variables;
3. Including treatment arm, age (≥ 65 or < 65 years), sex, BMI (≥ 35 kg/m² or < 35 kg/m²), race/ethnicity, material used in the TKA revision, and co-morbidities in the imputation model;
4. Creating five imputed datasets [Rubin 1996]⁷;
5. Combining completed-data estimates from five imputed datasets.

The mixed model analysis for both Global Physical Health and Global Mental Health described above will be repeated based on the imputed data.

8.7.4 30-Day Subject Incidence of SSC Analysis

The proportion of subjects with each value of “Occurred” or “No occurrences” or “Incomplete-Follow-up” for 30-Day SSC will be summarized, as applicable, by treatment arm based on the ITT, mITT analysis sets. Additionally, 30-Day SSC events by type: superficial SSI, deep SSI, dehiscence, seroma, hematoma, skin necrosis, or continued drainage will be summarized based on the mITT analysis set.

Superiority Testing

The following hypothesis will be tested for superiority:

Null H_0 : $\Delta_{\text{ciNPT-SOC}} = 0$

Alternative H_a : $\Delta_{\text{ciNPT-SOC}} \neq 0$

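### The multiple-imputation sensitivity analyses for pain, KOOS and PROMIS use only five imputations and list no revision type or clinical site, so borderline p-values are not reproducible and the imputation model omits terms of the analysis model

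*SAP*

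**What the plan says.** SAP 8.7.1 (pain), 8.7.2 (KOOS) and 8.7.3 (PROMIS Global-10) use the same recipe.

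- **Trigger.** Pain: "If an overall missing data rate for worst or average pain scores is 10% or greater". KOOS: "If a missing data rate for any subscale is 10% or greater". PROMIS: "If a missing data rate for Global Physical Health or Global Mental Health is 10% or greater".
- **Method.** Fully conditional specification (FCS) with linear regression, in SAS.
- **Imputation covariates.** Treatment arm, age group, sex and BMI group, followed by "race/ethnicity, material used in the TKA revision, and co-morbidities in the imputation model".
- **Number of imputations.** "Creating five imputed datasets", with a literature citation, and then "Combining completed-data estimates from five imputed datasets".
- **Analysis.** "The mixed model analysis described above will be repeated based on the imputed data". That model has arm, visit, their interaction, "revision type, clinical site, and with subject as a random effect".

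The SAP states no seed and no check of Monte Carlo error. It introduces the recipe as a basic description. SAP 7.3 classes these as sensitivity analyses for exploratory endpoints. SAP 8.7 says that exploratory analyses involving revision type use the actual type, and SAP 2.4 makes revision type the randomization stratum.

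**The concern.** There are two separate weaknesses.

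First, a multiple-imputation result is partly a random draw. With few imputations, a rerun under another seed can give a visibly different p-value. SAP 7.1 reports p-values to four decimals. By the visit schedules in SAP 4.3 there are 25 score-by-visit results: 2 pain scores × 2 post-baseline visits, 5 KOOS subscales × 3, and 2 PROMIS scores × 3, that is 4 + 15 + 6. Some may well be borderline.

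Second, an imputation model should contain at least the terms of the model fitted afterwards. If revision type and site are left out, imputed scores carry no effect of either factor beyond what the listed covariates convey, yet the mixed model adjusts for both.

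At stake is whether the check on missing data can be reproduced and is consistent with the model it checks.

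**Working it through.** The SAP derives nothing for the choice of five, so there is no figure to reproduce.

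**Inputs.** From the documents: m = 5, the 10% trigger, about 440 subjects and about 15 sites. Assumed: FMI of 0.1, 0.2 or 0.3. The 10% trigger is a missing-data rate, not an FMI; the two are close only if the other variables predict the score poorly.

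**Step 1. Seed noise.** Under Rubin's rules the SD of the pooled estimate over seeds, in units of its standard error, is about √(FMI/m). Relative efficiency against unlimited imputations is 1/(1 + FMI/m).

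| FMI | SD at m = 5 | Efficiency at m = 5 | SD at m = 50 |
|---|---|---|---|
| 0.1 | √(0.1/5) = 0.14 | 1/1.02 = 0.98 | √(0.1/50) = 0.04 |
| 0.2 | √(0.2/5) = 0.20 | 1/1.04 = 0.96 | √(0.2/50) = 0.06 |
| 0.3 | √(0.3/5) = 0.24 | 1/1.06 = 0.94 | √(0.3/50) = 0.08 |

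**Step 2. Effect on a borderline p-value.** Take z = 2 (two-sided normal p = 0.046) and move it by one SD each way.

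- m = 5, FMI 0.1: z from 1.86 to 2.14, p from 0.063 to 0.032.
- m = 5, FMI 0.3: z from 1.76 to 2.24, p from 0.079 to 0.025.
- m = 50, FMI 0.1: p from 0.051 to 0.041.
- m = 50, FMI 0.3: p from 0.054 to 0.038.

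These are one-SD ranges. Simulating the pooled estimate and its variance together (200,000 draws, complete-data df 400) gives central 95% ranges for a limiting p of 0.05. At m = 5 they are 0.025 to 0.108 (FMI 0.1) and 0.011 to 0.203 (FMI 0.3). At m = 50 they are 0.041 to 0.064 and 0.033 to 0.079.

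**Step 3. Omitted factors.** A simplified trial was simulated: one follow-up score, 440 subjects, 15 sites, half septic, 1,500 replicates. Assumed values were a revision-type effect of 0.60, a site SD of 0.4, a residual SD of 0.87 and no treatment effect.

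- *Missingness unrelated to arm or revision type.* With a fraction q imputed without revision type, its coefficient should shrink to about (1 − q) × 0.60, which is 0.54, 0.48 and 0.42 at 10%, 20% and 30% missing. The simulation gave 0.54, 0.48 and 0.42. With both factors in the imputation model it gave 0.60 to 0.61.
- *Treatment effect, missingness not depending jointly on arm and revision type.* No bias was seen; type I error was 0.030 to 0.049.
- *Treatment effect, missingness depending jointly on arm and revision type (assumed pattern).* Bias was −0.06, −0.10 and −0.14 at 10%, 20% and 30% missing, with type I error 0.07, 0.13 and 0.18. With both factors included, type I error was 0.05 to 0.06.

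**The case against.** The strongest reply is that nothing depends on these results. They run only when the 10% trigger is met and support exploratory endpoints. SAP 6 gives its alpha of 0.048 to the primary and secondary analyses only, and no decision rule uses these p-values. That stands and limits the importance of the point.

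It is also true that every finite m depends on the seed, that five imputations lose little efficiency, and that the FMI range is assumed. The only planning figure for loss is 5% to 10% (Protocol 8.4.2), so the upper end of the range has no support in the documents. But at FMI 0.1 the one-SD range still straddles 0.05, and efficiency does not measure reproducibility.

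A reader might infer that the omitted factors make the treatment comparison in these analyses unreliable. The documents do not support that. Arm is in the imputation model and randomization is stratified by revision type, so bias needs missingness that depends jointly on arm and the omitted factor. There is a possible route: repeat surgery through the incision forces withdrawal (Protocol 4.15), and no data are collected afterwards (Protocol 4.4.2). Nothing shows that this is large. The listed co-morbidities may also capture part of revision type, for example through prior infection of the operative site, but the SAP does not say which ones enter.

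A reader might also infer that baseline and other-visit scores are excluded. Under FCS the variables being imputed normally predict one another, and the recipe is presented as basic rather than complete. The silence is an ambiguity, not an exclusion.

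**Conclusion.** The point holds as a minor one about reproducibility and consistency between models. The SAP text fixes five imputations and lists neither revision type nor site. For an assumed FMI of 0.1 to 0.3, seed noise is about 0.14 to 0.24 standard errors, enough to carry a borderline p-value across 0.05 in either direction; fifty imputations reduce it to 0.04 to 0.08.

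The certain effect of the omission is on the coefficients of the omitted factors. For revision type this is an attenuation roughly in proportion to the share imputed, if the other covariates do not stand in for it. An effect on the treatment comparison is conditional on a missingness pattern that the documents do not establish, and its simulated size rests on assumed effects. The primary and secondary tests are untouched.

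**What to change.** In each of SAP 8.7.1, 8.7.2 and 8.7.3:

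1. Replace five imputations with at least 50 and pre-specify the seed.
2. Add actual revision type (the version SAP 8.7 uses for exploratory analyses) and clinical site to the imputation model.
3. State that the baseline score and the scores at the other visits are in the FCS variable set.

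The change needs no new data: these variables are already collected. It costs minutes of computing and a few lines of text. SAP 1 and 6 allow amendment before final database lock.

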8.7.2 KOOS Score Analysis

As described in Section 4.3.2 of this document, the KOOS has 5 subscales: Quality of Life (QOL), Sports and Recreation Function (Sport/Rec), Activities of Daily Living (ADL), Pain, and other Symptoms. For calculation purpose, the 2012 User’s Guide to: Knee injury and Osteoarthritis Outcome Score KOOS and KOOS Scoring 2012 will be followed and used for this study.

The KOOS consists of 42 items. Each item will be asked on a 5-point Likert scale and then will be converted to a numeric value as listed below:

SCALE	None	Mild	Moderate	Severe	Extreme
VALUE	0	1	2	3	4

All 5 subscales are scored separately and interpreted separately. According to the KOOS Scoring 2012, at least 50% of the items should be responded by each patient in order to calculate the subscale for the subject based on the minimum required non-missing items listed in the table below. For each subscale, if more than 50% of the subscale items for a subject are omitted, then the calculated score for the subject will be considered missing in the subscale since there will be no imputation for any omitted/non-responded item.

SUBSCALES	QOL	Sport/Rec	ADL	Pain	Symptoms
# of Non-missing Items	2	3	9	5	4
Total Number of Items	Q1 – Q4	SP1 – SP5	A1 – A17	P1 – P9	S1 – S7

Each subscale score will be normalized by applying the mean of the observed items within the subscale, divided by 4, and multiplying by 100, and then subtracted from 100. i.e.

1. KOOS QOL = 100 – Mean score (Observed Q1 to Q4) * 100 / 4
2. KOOS Sport/Rec = 100 – Mean score (Observed SP1 to SP5) * 100 / 4
3. KOOS ADL = 100 – Mean score (Observed A1 to A17) * 100 / 4
4. KOOS Pain = 100 – Mean score (Observed P1 to P9) * 100 / 4
5. KOOS Symptoms = 100 – Mean score (Observed S1 to S7) * 100 / 4

For each subscale, the range of a normalized score will be from 0 (0 indicating extreme symptoms / problems) to 100 (100 indicating no symptoms / problems). For change from baseline, a positive value indicates fewer symptoms / problems post-baseline as compared with baseline; a negative value indicates more symptoms / problems post-baseline as compared with baseline.

The normalized scores and change from baseline for each subscale will be summarized by treatment arm and by visit. Change from baseline for normalized scores for each subscale will be analyzed using a mixed model, which includes fixed effects (“Treatment Arm” and “Visit”) plus the interaction term (“Treatment Arm by Visit”), revision type, clinical site, and with subject as a random effect. LS means along with 95% confidence intervals and p-values at each post-baseline timepoint will be presented.

If a missing data rate for any subscale is 10% or greater, then an approach of multiple imputation based on Rubin’s [1976, 1987]^{3,4} for missing data for all subscales will be used by creating several different plausible imputed data sets and appropriately combining results obtained from each of them.

A basic description of the multiple imputation includes:

1. Using SAS procedures including Proc MI and Proc MIANALYZE;
2. Using the fully conditional specification (FCS) method / algorithm [Brand 1999 and van Buuren 2007]^{5,6} which is a linear regression for continuous variables;
3. Including treatment arm, age (≥ 65 or < 65 years), sex, BMI (≥ 35 kg/m² or < 35 kg/m²), race/ethnicity, material used in the TKA revision, and co-morbidities in the imputation model;
4. Creating five imputed datasets [Rubin 1996]⁷;
5. Combining completed-data estimates from five imputed datasets.

The mixed model analysis for each subscale described above will be repeated based on the imputed data.

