8.3.6. Exploratory Endpoints

In general, analyses will be performed on subjects in the ITT and/or mPP Analysis Sets using methods outlined in section 8.3.1. The number of subjects in each treatment arm at each scheduled visit with adequate assessments will be summarized for each visit. Assessments performed outside the scheduled visit windows may not be included in the models but will be listed separately. The patterns of missing data will be presented using

descriptive analyses. Other statistical analyses exploring the effects of imputation methods for non-response may be generated as appropriate.

Because the analyses are exploratory, no adjustment will be made for multiple comparisons. Confidence intervals may not be created for subsets with less than ten subjects, although standard errors or deviations will be presented to provide a measure of variability. Complete details for all endpoints will be outlined in the Statistical Analysis Plan.

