2.5 Schedule of Events and Visits

A detailed schedule of events and visits for the study is provided in Table 1.

Table 1: Schedule of Events

V2.0 August 8, 2019

	Screening	TKA Revision		End of Treatment	Midterm Follow-up	Long Term Follow-up	Unscheduled
		Pre	Post				
	Day -30 to 0	Day0	Day0	Per Dressing IFU	Day 30-45	Day 90 (+14 days)	
Informed Consent	X						
Pre-Operative Inclusion & Exclusion Criteria	X						
Demographics & Subject Characteristics	X						
Vital Signs	X	X ²					
Medical & Surgical History	X	X ³					
Laboratory Assessment for Pregnancy ¹	X	X					
Intra-operative Inclusion & Exclusion Criteria			X				
TKA Revision Procedure			X				
Randomization			X				
Application of Study Treatment			X				
Removal of Study Treatment				X			
SSC Assessment				X	X	X	X
Intervention Assessment				X	X	X	X
Pain Assessment		X	X ⁴	X			
Patient-Reported Outcomes Assessments (KOOS and PROMIS Global-10)	X			X	X	X	
Healthcare Utilization Assessment				X	X	X	X
End of Study						X	X ⁵
Concomitant Medications	X	X	X	X	X	X	X
Adverse Event Assessment and SAE Reporting			X	X	X	X	X

1 - Assessed on women of child-bearing potential
2 - Weight only
3 - Updates to medical and surgical history to be documented.
4 - Pain will be assessed at the earlier of discharge or 24 hours (± 2 hours) after the TKA Revision.
5 - End of Study assessed at an unscheduled visit only when a subject discontinues prior to the 90-day visit.

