4.3.1 Pain Assessment

- Worst pain last 24 hours
- Average pain in last 24 hours

The pain assessment consists of two self-administered questions used to evaluate the severity of a subject's pain in the past 24 hours post TKA revision.

Subjects will respond using the integer value. All efforts will be made to ensure the subject completes both pain assessments at each scheduled visit: Day 0 pre-TKA revision, Day 0 post-TKA revision and End of Treatment.

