4.3.2 Knee Injury and Osteoarthritis Outcome Subscale Score (KOOS)

The KOOS instrument is a patient-reported questionnaire to assess short-term and long-term symptoms and functions. KOOS consists of 5 subscales:

- KOOS: Knee-Related Quality of Life (QOL)
- KOOS: Sport and Recreation Function (Sport/Rec)
- KOOS: Activities of Daily Living (ADL)
- KOOS: Pain
- KOOS: Other Symptoms

The scoring details are in Section 8.7.2. All efforts will be made to ensure the subjects complete the entire assessment at each scheduled visit: Baseline (Screening or Day 0), End of Treatment, Midterm Follow-up, and Long-Term Follow-up.

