8.7 Exploratory Endpoint Analyses

In general, analyses listed below will be performed on subjects in the ITT analysis set unless otherwise specified. Analyses including revision type will be based on per actual revision type.

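### The pain, KOOS and PROMIS models name a random subject effect and no residual covariance, so their per-visit intervals will be mis-sized if spread differs between visits

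*SAP*

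**What the plan says.** SAP 8.7.2 analyses change from baseline in each KOOS subscale with a mixed model containing arm, visit, arm by visit, "revision type, clinical site, and with subject as a random effect". Sections 8.7.1 (worst and average pain) and 8.7.3 (PROMIS physical and mental health) use the same words. The reported output in 8.7.2 is: "LS means along with 95% confidence intervals and p-values at each post-baseline timepoint will be presented". The other two sections promise the same. None of the three names a residual covariance structure, a robust standard error or a degrees-of-freedom method.

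The visits differ by instrument. SAP 4.3.2 lists KOOS at "Baseline (Screening or Day 0), End of Treatment, Midterm Follow-up, and Long-Term Follow-up", and 4.3.3 lists the same visits for PROMIS, so each has three post-baseline visits. SAP 4.3.1 lists pain at "Day 0 pre-TKA revision, Day 0 post-TKA revision and End of Treatment", so pain has two. The schedule in SAP 2.5 fixes the first of these: "Pain will be assessed at the earlier of discharge or 24 hours (± 2 hours) after the TKA Revision".

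On the analysis set, SAP 8.7 says that "analyses listed below will be performed on subjects in the ITT analysis set unless otherwise specified". On multiplicity, Protocol 8.3.6 says: "Because the analyses are exploratory, no adjustment will be made for multiple comparisons". If 10% or more of the data are missing, all three sections add multiple imputation and then repeat the same mixed model.

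**The concern.** With a random subject intercept and nothing else, every observation has the same total variance, whatever the visit. Each visit's standard error is therefore built from a variance pooled over visits. That does little harm to a comparison averaged over visits, but these sections report visit by visit.

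Equal spread should not be taken for granted. KOOS and PROMIS run from the end of dressing treatment, through Day 30-45, to about three months after revision surgery. Pain runs from at most about 24 hours after surgery to the end of treatment. If spread differs, intervals at the more variable visits are too short and their p-values too small, while the less variable visits lose power. Nine scores are affected: two pain, five KOOS and two PROMIS. SAP 1 allows the planned analyses to go into manuscripts and regulatory submissions, so even unadjusted exploratory p-values should have the level they claim.

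**Working it through.** **Inputs.** The model, visits and output come from the sections cited above. The documents give no SD, correlation, sample size or power for these scores, so there is no stated figure of the plan's own to reproduce on this point. The only stated size, 199 per arm in SAP 2.1, is for the primary endpoint. It does reproduce (20% against 10%, two-sided 0.05, 80% power gives 199), and I use it below only as a realistic size. All SDs are assumptions. Only their ratios matter, so the three-visit lines serve KOOS and PROMIS alike.

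**Formula.** With complete data, the random-intercept total variance equals the mean of the visit variances:

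SD_pooled = √(mean of SD_visit²)

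The model's standard error at a visit is the correct one multiplied by SD_pooled / SD_visit, for an arm mean or an arm difference. Hence

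coverage = 2Φ(1.96 × SD_pooled / SD_visit) − 1.

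**Numbers.**
- 18/20/22: √((324 + 400 + 484)/3) = √402.67 = 20.07
- 15/18/22: √((225 + 324 + 484)/3) = √344.33 = 18.56
- Pain 3.0/2.4: √((9.00 + 5.76)/2) = √7.38 = 2.717

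| Assumed SDs of change | SD_pooled / SD_visit | Coverage, % | False-positive rate, % |
|---|---|---|---|
| Three visits, 20/20/20 | 1.000 / 1.000 / 1.000 | 95.0 / 95.0 / 95.0 | 5.0 / 5.0 / 5.0 |
| Three visits, 18/20/22 | 1.115 / 1.003 / 0.912 | 97.1 / 95.1 / 92.6 | 2.9 / 4.9 / 7.4 |
| Three visits, 15/18/22 | 1.237 / 1.031 / 0.843 | 98.5 / 95.7 / 90.2 | 1.5 / 4.3 / 9.8 |
| Pain, 2.5/2.5 | 1.000 / 1.000 | 95.0 / 95.0 | 5.0 / 5.0 |
| Pain, 3.0/2.4 | 0.906 / 1.132 | 92.4 / 97.3 | 7.6 / 2.7 |

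In the 15/18/22 case the Day 90 interval is 16% too narrow and the End of Treatment interval 24% too wide. Reversing the order of the SDs mirrors the results, and the documents do not indicate which order to expect.

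**Simulation check.** I simulated 199 per arm, three visits, and assumed correlations of 0.6 (visits 1 and 2), 0.3 (1 and 3) and 0.7 (2 and 3), with 1,500 runs per scenario.
- SDs 15/20/25, complete data: the random intercept covers 99.6/95.9/90.3% and unstructured covariance 95.3/95.8/95.9%.
- The same SDs with about 12% of Day 90 values lost to dropout that depends on the previous score: 99.2/94.9/89.5% against 95.2/94.9/96.3%.
- SDs 25/20/15, complete data: 90.5/96.1/99.4% against 95.9/95.5/96.2%.
- Equal SDs with the same unequal correlations: the random intercept covers 94.3 to 95.3% with complete data and 94.1 to 95.3% with about 13% dropout.

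The last line isolates the cause. Assuming one correlation does not disturb per-visit coverage here; assuming one variance does.

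**The case against.** A reader might go further and infer that the per-visit intervals are wrong as planned. The documents do not support that. The error exists only if SDs differ by visit, no SD is given, and with equal SDs the intervals are correct. The SAP also does not rule out a residual structure alongside the random effect. Its silence makes the random intercept the natural reading, not a certain one.

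Three further stretches should be avoided.
- The visits do not run to Day 90 for every score. Pain stops at End of Treatment.
- The single correlation is not what distorts coverage, as the equal-SD simulation shows.
- Bias from a wrong correlation structure under dropout is possible in principle, but its size depends on arm-specific dropout that the documents do not describe. Under assumed correlations of 0.6/0.3/0.7 and about 11% dropout, the Day 90 arm difference moved by roughly 0.2 to 1.3 points. The largest shift needed dropout running in opposite directions in the two arms. This is at most a secondary argument.

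The strongest objection is about consequence. There are 2×2 + 5×3 + 2×3 = 25 visit-level comparisons, all exploratory and unadjusted. Error is moved between visits more than it is added: the average false-positive rate over visits is about 5.1% for 18/20/22, 5.2% for 15/18/22 and 5.1% for pain. The planned descriptive tables would also expose unequal spread, since for KOOS "The normalized scores and change from baseline for each subscale will be summarized by treatment arm and by visit", and SAP 7.1 includes the SD in such summaries. All of this stands and keeps the severity low. It does not remove the point. Visible SDs do not correct a reported p-value, and the imputation step repeats the same model.

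**Conclusion.** The point holds in conditional form. Read as written, SAP 8.7.1 to 8.7.3 assume equal variance across visits while promising inference at each visit. If the SD of change varies modestly (18/20/22), coverage at the most variable visit falls to 92.6%. With a wider range (15/18/22) it falls to 90.2%, a false-positive rate of 9.8% instead of 5%, while the least variable visit is over-covered at 98.5%. For pain SDs of 3.0/2.4, coverage is 92.4% and 97.3%. These figures rest on assumed SDs and on complete data; the simulation gives a similar picture with moderate dropout. Severity is low: nine exploratory scores are affected, and no primary, secondary or safety conclusion depends on them.

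**What to change.** In SAP 8.7.1, 8.7.2 and 8.7.3, replace the random subject effect with a repeated-measures model with unstructured covariance across the post-baseline visits (in SAS, REPEATED visit / SUBJECT=subject TYPE=UN) and Kenward-Roger degrees of freedom. Use the same model when the analysis is repeated on imputed data.

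Name a fallback for non-convergence in the three-visit KOOS and PROMIS models only: heterogeneous Toeplitz (five parameters) or heterogeneous compound symmetry (four). With two pain visits, both are identical to unstructured, so neither is a fallback there.

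The cost is about one line of code per model. Covariance parameters rise from two to three for pain and from two to six for KOOS and PROMIS, which is negligible with about 400 subjects. If the SDs turn out equal, almost nothing is lost.
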